In rat models, baclofen dose-dependently reduced heroin-seeking behavior [Spano et al, 2007], reversed behavioral sensitization to morphine [Bartoletti et al, 2007] and prevents heroin-induced reinstatement of heroin-seeking behaviors [Spano et al, 2007] and enhances extinction of opiate and methamphetamine-induced conditioned place preference [Heinrichs et al, 2010; Voigt et al, 2011] particularly stress-accenuated morphine-induced conditioned place preference [Meng et al, 2014]. In rodent models of cocaine- or heroin-seeking behaviors, baclofen was found to attenuate these behaviors [DiCiano and Everitt, 2003]. Similar results are noted for alcohol-seeking and drinking behavior [Maccioni and Colombo, 2009].

Baclofen reduced ethanol consumption in mice, but only in those which were phenotypically less prone to heavy drinking behaviors [Villas Boas et al, 2012]. Baclofen reduced nicotine- [Paterson et al, 2004] and morphine self-administration in rats and a GABA(B)-antagonist increased morphine administration [Ramishini et al, 2013]

Baclofen administered into the locus coeruleus attenuated morphine withdrawal signs [Riahi et al, 2009]

Presumed mechanisms for baclofen's actions on addictive behaviors is an interaction wth dopaminergic neurons of the ventral tegmental area where baclofen leads to Girk signaling [Arora et al, 2011] with a subsequent reduction in dopamine release in the nucleus accumbens.

**Baclofen toxicology and drug/drug interactions.** There have been limited toxicities or side effects of baclofen. Odd reactions include things such as the induction of hiccup-like respirations [Srivasta et al, 2014] or diabetes insipidus [Silversides and Scott] In rats, intraventricular baclofen impaired memory [Zarrindast et al, 2001] CB1 receptor antagonism decreases analgesia due to baclofen and GABA(B) antagonists reduce analgesia due to cannabinoids [Naderi et al, 2005].

Most toxicity reports relate to withdrawal [Ross et al, 2011] or excessive dosing [Roy and Wakefield, 1986; Leung et al 2006] with CNS effects predominant (loss of consciousness, delirium, hypertension). Because it is kidney-cleared, toxicity is more common in patients with advanced nephropathy [El-Husseini et al, 2011]

Some increases in depression have been noted, but in the spinal cord injury patients, use of baclofen improved psychiatric symptoms [Margetis et al, 2014]

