#### 6.0 STUDY INTERVENTIONS/PROCEDURES

- Study design: Placebo-controlled double-blind
- Comparison groups (for prospective and clinical trials only).

Placebo treated individuals

- Timeline of interventions (for prospective and clinical trials only).

Patients will be recruited preoperatively by Drs. [name] and [name], in addition to anesthesiology-related personnel in the KPAC. Informed consent will be obtained at that time. On the Day of Surgery, subjects will be contacted by study personnel in the Preoperative Holding area to confirm patient participation and then a randomization envelope containing a single dose of either baclofen or placebo will be opened (Groups 1&2 intermixed; Groups 3&4 intermixed; envelopes will be prepared ahead of time by a different investigator according to a randomization table). Subjects will then consume the pill in the envelope and this will be recorded. Patients will then be treated intraoperatively and postoperatively according to the standard of care associated with these surgeries but with an attempt to utilize consistent doses of intraoperative opioids other agents across groups and standardized PACU orders. After discharge from the

PACU patients' pain will be treated with PCA morphine. Notably, the treating anesthesiologist and all PACU personnel will be blinded to the drug that was administered preoperatively. The total use of analgesics, measures of any other side effects (nausea, excessive sedation) will be recorded for 24 hours.

- **Measured Outcomes:**
  - a. Primary outcomes: Postoperative opioid consumption (measured as OMEs)
  - b. Secondary outcomes: Incidence of nausea/vomiting; excessive sedation per patient self assessment; any other untoward events

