#### **8.0 DRUG INFORMATION**

Drug Name:	baclofen hydrochloride
Classification:	Antispastic; GABA-B receptor agonist
Mode of Action:	GABA-B receptor agonist
Storage and Stability:	Pharmacologically stable
Metabolism:	Cleared unchanged through kidneys; half-life 2-4 hours
Preparation:	Pill
Administration:	Oral
Incompatibilities:	None

• Contraindications: allergy to baclofen

• Precautions: very safe medication with long track record of clinical use

	

[Click here to enter text.](#)

**Side Effects:** Adverse effects indicated in *italics* are the most frequent adverse effects. Adverse events in **bold** are severe/life-threatening, otherwise they are mild to moderate in reaction.

CNS: *sedation, mild*

CV: *no major*

EENT: *no major*

ENDO: *no major*

GI: *no major*

GU: *no major*

INTEG: *no major*

MS: *weakness at excessive doses*

Investigational New Drug (IND) Application required (check yes or no):  Yes  No

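### Excessive sedation is defined by patient self-assessment, with no observer rating and no rule for patients too sedated to answer, so events may be missed and the arm comparison weakened

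*Combined protocol and SAP*

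**What the plan says.** Section 6.0, under the measured outcomes, lists "excessive sedation per patient self assessment" as a secondary outcome, next to nausea and vomiting and "any other untoward events". The timeline in the same section says that "measures of any other side effects (nausea, excessive sedation) will be recorded for 24 hours", but does not say who records them or with what instrument. It also states that "all PACU personnel will be blinded to the drug that was administered preoperatively"; the treating anesthesiologist is blinded too. After PACU discharge, pain in both arms is treated with PCA morphine.

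Section 8.0 explains that the italicised effects "are the most frequent adverse effects". Its CNS entry is "sedation, mild" and its musculoskeletal entry is "weakness at excessive doses". Section 2.0 describes baclofen toxicity "with CNS effects predominant (loss of consciousness, delirium, hypertension", and says that most such reports concern withdrawal or excessive dosing. Section 9.0 assigns Fisher's exact test to categorical incidence data.

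**The concern.** The condition being measured impairs the instrument that measures it. A patient who is hard to rouse or confused cannot rate their own sedation at that moment, and recall of that period may be poor. Missing or unreliable answers may therefore gather in the patients who have the event. The plan does not say whether such a patient counts as an event, as a non-event or as missing.

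What is at stake is the safety comparison. Section 7.0 gives efficacy, safety and tolerability as the longer-term goal, leading to a follow-up study with baclofen given for up to two weeks after surgery. A weak sedation comparison could be read as reassurance when that study is planned. Blinded staff who could observe sedation directly are already part of the trial, but the outcome definition gives them no role.

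**Working it through.** **What the text settles.** Three points can be read directly.

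- Section 6.0 names one method for sedation: self-assessment.
- The sentence on 24-hour recording and the open category of untoward events name no rater, scale, cut-off or time point. They leave staff recording possible but do not specify it.
- The Section 4.0 exclusion for limits on reporting concerns postoperative pain. It does not deal with sedation that arises after dosing.

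**There is no stated figure to reproduce.** The document gives no sedation rate, alpha, power or accuracy of self-report. The rest is illustration.

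**Inputs.** Section 5.0 plans 4 groups of 20, so pooling the strata gives 2 × 20 = 40 per arm. The test is Fisher's exact (Section 9.0). Assumed: two-sided 5% level, the true sedation rates, and the share of events missed.

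**Formulas.** With no false reports, observed rate = true rate × (1 − share missed). Power = Σ over all pairs (a, b) of Bin(a; 40, p_B) × Bin(b; 40, p_P), counting the pairs with Fisher p ≤ 0.05 and more sedation on baclofen. Missed events are counted as non-events unless stated otherwise.

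**Equal loss in both arms**

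| True rates (baclofen v placebo) | Share missed | Observed | Difference | Power |
|---|---|---|---|---|
| 40% v 10% | 0 | 40% v 10% | 30 points | 85% |
| 40% v 10% | 25% | 30% v 7.5% | 22.5 points | 68% |
| 40% v 10% | 50% | 20% v 5% | 15 points | 41% |
| 30% v 10% | 0 | 30% v 10% | 20 points | 53% |
| 30% v 10% | 50% | 15% v 5% | 10 points | 18% |

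Equal loss leaves the risk ratio unchanged (40/10 = 20/5 = 4; 30/10 = 15/5 = 3). It shrinks the risk difference and the power.

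**Loss in the baclofen arm only, true 40% v 10%.** The expected counts are 16 of 40 and 4 of 40.

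- If 4 of the 16 are lost and counted as non-events: 12/40 v 4/40 = 30% v 10%, power 53%. If those 4 are treated as missing: 12/36 v 4/40, power 64%.
- If 8 of the 16 are lost and counted as non-events: 8/40 v 4/40 = 20% v 10%, power 16%. If those 8 are treated as missing: 8/32 v 4/40, power 32%.

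The unstated rule for non-responders therefore matters: the same patients give 53% or 64%, and 16% or 32%.

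**Over-reporting.** Take true 30% v 10%, sensitivity 90% and specificity 80%. Observed on baclofen: 0.30 × 0.90 + 0.70 × 0.20 = 0.41. Observed on placebo: 0.10 × 0.90 + 0.90 × 0.20 = 0.27. Both counts rise, the difference falls from 20 to 14 points, and power falls from 53% to 19%. So self-report need not under-count in order to weaken the comparison.

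**The case against.** Four points can be made for the plan.

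- **Staff recording is not excluded.** Excessive sedation is among the side effects to be recorded over 24 hours, and an unrousable or delirious patient could appear as an untoward event. A reader might infer that self-report is the only possible source and that staff are shut out. The document does not say that; it leaves the recorder unnamed. What stands is that self-assessment is the only named method and sits in the outcome definition itself.
- **The risk may be small.** The trial gives a single 10 mg dose, Section 8.0 calls the sedation mild, and Section 2.0 ties most toxicity reports to withdrawal or excessive dosing. A reader might carry loss of consciousness and delirium over to this trial, or call sedation the only frequent effect listed. Neither is supported: weakness is italicised too, though limited to excessive doses. This lowers the stakes but leaves the measurement gap.
- **The direction is unknown.** A reader might conclude that baclofen's sedation is under-counted. With a half-life of 2–4 hours and a 24-hour window, a patient could report later, and recall can err either way. Both arms receive PCA morphine. If the trial's hypothesis holds, placebo patients use more opioid, so non-response could rise in that arm as well. This objection stands in full.
- **Sample size limits this comparison anyway.** With perfect ascertainment, 30% v 10% has only 53% power. True, but that is a reason not to lose more information.

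Self-report is also a legitimate tolerability measure, so it should be kept.

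**Conclusion.** The concern holds in a limited form. Excessive sedation is defined by self-assessment alone among named methods, without an observer rating or a rule for patients who cannot answer. Following the plan as written may lose or misclassify events in the patients most affected, and may weaken the arm comparison. That sedation is in fact under-counted, or that the bias runs in a known direction, is not established.

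The power figures show only what is possible. The fall from 85% to 41% assumes true rates of 40% v 10%, half the events missed in both arms, missed events counted as non-events, 40 per arm, and a two-sided 5% test. None of the rates or loss fractions comes from the document. Arm-specific loss is not needed for the comparison to suffer. This is one secondary safety outcome and the primary analysis of opioid consumption is untouched, so the change is worth making but not critical to the trial's main result.

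**What to change.** Amend the secondary outcome in Section 6.0 as follows.

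1. Add an observer-rated sedation measure on a named scale, with the cut-off for excessive sedation fixed in advance.
2. Have it charted at existing observation times over the 24 hours by the PACU personnel, who are already stated to be blinded. Extend this to ward staff only if they are kept blinded as well, since the document does not say that they are.
3. State that a patient who cannot self-assess because of sedation or confusion counts as an event, and have the reason for any missing self-assessment recorded.
4. Keep patient self-assessment as a separately reported tolerability measure.

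The cost is an amended outcome definition, a chart field, minor extra chart abstraction and a second sedation figure to report. The document does not say that sedation is charted routinely, so the site should confirm this before relying on existing records.

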#### **7.0 PLAN FOR STUDY:** [Click here to enter text.](#)

- a. What is the potential impact of your study findings (e.g., how will findings impact clinical outcomes)? Baclofen may prove beneficial as a perioperative analgesic adjuvant – the long term goal would be to determine potential efficacy, safety and tolerability of baclofen use and to perform a follow-up study in which baclofen would be co-administered postoperatively for up to 2 weeks. The conversion from acute to chronic pain and the potential anti-reward effects produced by baclofen could impact subsequent opioid use and abuse.
- b. Do you plan to submit an abstract based on this project?  Yes  No (If yes, to which meeting venue? [Click here to enter text.](#))
- c. Do you intend to publish the finding from this research project:  Yes  No

#### **8.0 DRUG INFORMATION**

Drug Name:	baclofen hydrochloride
Classification:	Antispastic; GABA-B receptor agonist
Mode of Action:	GABA-B receptor agonist
Storage and Stability:	Pharmacologically stable
Metabolism:	Cleared unchanged through kidneys; half-life 2-4 hours
Preparation:	Pill
Administration:	Oral
Incompatibilities:	None

• Contraindications: allergy to baclofen

• Precautions: very safe medication with long track record of clinical use

	

[Click here to enter text.](#)

**Side Effects:** Adverse effects indicated in *italics* are the most frequent adverse effects. Adverse events in **bold** are severe/life-threatening, otherwise they are mild to moderate in reaction.

CNS: *sedation, mild*

CV: *no major*

EENT: *no major*

ENDO: *no major*

GI: *no major*

GU: *no major*

INTEG: *no major*

MS: *weakness at excessive doses*

Investigational New Drug (IND) Application required (check yes or no):  Yes  No

## **9.0 STATISTICAL CONSIDERATIONS**

- Original Plan for Statistical Analysis : Data analysis will be by ANOVA analysis using Tukey's HSD for post-hoc analysis for primary outcome data and Fishers Exact test for categorical incidence data. A mid-point analysis was proposed after the study of 40 subjects.

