## 1.0 SUMMARY OF STUDY

The present study proposes to study the effect of a single preoperative dose of baclofen on pain treated in the first 24 hours after kidney stone-related surgeries using a placebo-controlled, double-blind methodology. Because this patient population often has a history of significant opioid use, which would be expected to alter postoperative pain medication requirements, patients will be stratified into those which would be expected to be opioid tolerant (use >30 OME daily) and those who are generally opioid naïve.

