### **3.0 OBJECTIVE(S) & HYPOTHESIS**

Purpose of study:

To determine whether a single, oral dose of baclofen alters postoperative opioid requirements

Study Hypothesis:

We hypothesized that a single, oral dose of baclofen given to patients undergoing kidney stone surgery will reduce postoperative opioid requirements measured in the PACU and in the first 24 hours following surgery.

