#### 5.0 RANDOMIZATION/RECRUITMENT DETAILS (If applicable)

- Randomization groups, how will subjects be randomized:

All subjects who are patients of Drs. [name] and/or [name] and scheduled for kidney stone-related surgery will be potentially recruited.

Part 1: In an initial open run-in period, six patients will be recruited and given a dose of 10 mg baclofen preoperatively so that potential side effects can be assessed in an unblinded fashion.

Part 2: After that, patients will be identified and initially stratified into two groups based on preoperative opioid use. If daily using >30 Oral Morphine Equivalents (OMEs) for more than one month they will be designated as Opioid Tolerant. Otherwise, they will be included in the Opioid Naïve group. These two groups will then be each randomized (envelope assignment) into receiving either baclofen (10 mg, p.o. x 1) or placebo as a preoperative medication such that there will be 4 groups of 20 patients identified:

Group 1: Opioid Tolerant – baclofen

Group 2: Opioid Tolerant – placebo

Group 3: Opioid Naïve – baclofen

Group 4: Opioid Naïve - placebo

- Blinded  Yes  No (Single  Double  please check box).

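### Section 9 does not say which ANOVA test decides the single baclofen hypothesis: the 40 v 40 treatment effect and 20 v 20 Tukey contrasts both fit the wording and can give opposite answers

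*Combined protocol and SAP*

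**What the plan says.** Section 3 (Objectives and Hypothesis) makes one statement for the whole population, that "a single, oral dose of baclofen given to patients undergoing kidney stone surgery will reduce postoperative opioid requirements". Section 6 (Study Interventions/Procedures) gives one comparison group: "Placebo treated individuals". Section 5 stratifies patients as Opioid Tolerant or Opioid Naïve and randomises baclofen or placebo within each stratum, "such that there will be 4 groups of 20 patients identified". Section 1 explains the stratification by a "history of significant opioid use, which would be expected to alter postoperative pain medication requirements".

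Section 9 (Statistical Considerations) is the only statistical text. For the primary outcome it says "Data analysis will be by ANOVA analysis using Tukey's HSD for post-hoc analysis for primary outcome data". It names no ANOVA factors, interaction term, deciding contrast or significance level. It is labelled as the original plan, and the documents contain no later one.

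**The concern.** Three tests fit the sentence in Section 9, and they answer different questions.

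1. A two-way ANOVA (treatment, opioid stratum), decided by the treatment effect: 40 v 40, stratum-adjusted.
2. A four-group ANOVA, decided by Tukey's HSD. Four groups give six pairwise comparisons. Two are baclofen v placebo within a stratum (20 v 20). The other four cross the opioid strata and do not bear on the hypothesis. Nothing says whether one or both of the relevant contrasts must be significant.
3. The overall F over four groups, which does not isolate baclofen.

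Tukey's HSD has a role only with more than two groups. Naming it therefore makes the second reading a live one, although the documents do not state it. The same 80 patients could give a positive or a negative trial depending on a choice left until the data are in.

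**Working it through.** **Inputs.** From Section 5: 4 × 20 = 80 randomised patients (the six open run-in patients are separate), so 40 v 40 pooled and 20 v 20 within a stratum. The documents give no alpha, power, SD or expected effect, so there is no power figure of the plan's own to reproduce. Assumed here: two-sided 5% (familywise for Tukey), equal SDs unless stated, no dropout, effects d in SD units, pooled error with 80 − 4 = 76 df.

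**Critical values.** Treatment effect: t(0.975; 76) = 1.992. Tukey: q(0.95; 4, 76)/√2 = 3.715/1.414 = 2.627, a per-comparison p of 0.0104.

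**Power formula.** Noncentral t with noncentrality d√(n/2), n per arm. At d = 0.64:
- treatment effect: 0.64 × √20 = 2.86, power 81%;
- one given Tukey contrast: 0.64 × √10 = 2.02, power 28%.

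**Effect detectable with 80% power.** Treatment effect 0.63 SD; unadjusted 20 v 20 contrast 0.90 SD; Tukey contrast 1.10 SD. The step from 0.63 to 0.90 is the halved sample, and the step from 0.90 to 1.10 is the Tukey penalty.

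**Effect common to both strata** (1,000,000 simulated trials per row):

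| d | Treatment effect, 5% | At least one Tukey contrast | Both Tukey contrasts | Treatment effect, 2.1% | Two contrasts, 2.5% each | Treatment effect (5%) and at least one Tukey contrast disagree |
|---|---|---|---|---|---|---|
| 0.5 | 60% | 28% | 3% | 45% | 43% | 34% |
| 0.64 | 81% | 48% | 8% | 69% | 64% | 34% |
| 0.8 | 94% | 71% | 22% | 89% | 83% | 24% |
| 1.0 | 99% | 91% | 50% | 98% | 96% | 9% |

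With no baclofen effect, at least one of the two Tukey contrasts is significant in 2.1% of trials, against 5% for the treatment effect. Two columns therefore match the error rates. Compare the treatment effect at 2.1% with at least one Tukey contrast, and two contrasts at 2.5% each with the treatment effect at 5%. For a common effect the treatment effect stays ahead both ways. Disagreement is near its peak at 0.5 to 0.64 SD; it is 5% at 0 SD and 2% at 1.2 SD.

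**Overall F.** With a 1 SD stratum difference and no baclofen effect, the noncentrality is 20 × 4 × 0.5² = 20. With 3 and 76 df the test is significant in 97% of trials.

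**Effect in one stratum only.** The pooled effect is halved, so at 0.8 SD the noncentrality is 0.4 × √20 = 1.79.

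| d in that stratum | Treatment effect | That stratum's Tukey contrast | Two within-stratum tests, 2.5% each |
|---|---|---|---|
| 0.8 | 42% | 47% | 59–61% |
| 1.0 | 60% | 70% | 80–81% |

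(The ranges are for own-stratum and pooled variance.)

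**Unequal SDs, same absolute OME saving of 0.64 Naïve SD.** If the Tolerant SD is twice the Naïve SD, the pooled SD is √((4+1)/2) = 1.58 and the effect is 0.64/1.58 = 0.40 pooled SD; equal-variance treatment-effect power is 43%. At three times, the pooled SD is √((9+1)/2) = 2.24, the effect is 0.29 and power is 25%. Two within-stratum tests at 2.5% each, using each stratum's own variance, have 45% and 42%.

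**The case against.** The strongest reply is that Section 9 makes ANOVA the analysis and Tukey only the follow-up. With two treatments randomised within two strata, one hypothesis and one comparator, the ordinary reading is then a treatment-by-stratum ANOVA decided by the 40 v 40 effect. This stands to the extent that the halved sample is conditional. A reader might infer that the plan commits to 20 v 20 tests; the documents do not say so. They do not commit to the treatment effect either, and that gap is the point.

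A reader might also infer that the treatment effect is the better test in general. That does not hold. For an effect in one stratum only, error-matched within-stratum tests gain about 17 to 21 percentage points. Under strongly unequal SDs, an equal-variance treatment effect can fall behind within-stratum tests that use their own variances. The 2.1% error rate for the Tukey contrasts also depends on equal SDs: at an SD ratio of 3 it is about 5.6%.

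Finally, the equal quotas of 20 per cell are consistent with interest in each stratum separately. Pooled or stratum-specific is the sponsor's choice, but Section 3 as worded is a pooled statement.

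**Conclusion.** The point holds in this form: the factors and the deciding test are missing, and the choice between permissible readings can reverse the result. If the Tukey contrasts decide, a mid-range effect common to both strata is often missed: at 0.64 SD, 48% power (at least one) or 8% (both) against 81%, with about 34% disagreement. For very small or very large effects the choice matters little. The overall F cannot decide the hypothesis. All power figures are illustrations under an assumed two-sided 5%, assumed effects and equal SDs; the 20 per cell comes from the protocol. This should be fixed, but it does not make the data unusable.

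**What to change.** Before any unblinding, state in Section 9:

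- The primary test of the Section 3 hypothesis is the baclofen v placebo difference adjusted for opioid stratum, in all 80 randomised patients, two-sided 5%, with a 95% CI.
- Variances may differ between strata. For example, use stratum-specific variances with inverse-variance weighting, or a transformation chosen in advance.
- The treatment-by-stratum interaction and both within-stratum estimates with CIs are secondary. Tukey comparisons may stay as secondary.

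If the sponsor wants separate stratum conclusions instead, make the two within-stratum contrasts primary at 2.5% each and drop the cross-stratum Tukey comparisons. If unblinding has already occurred, which the documents do not settle, label the choice post hoc.

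The cost is one paragraph, with no new patients or data. The price of the pooled test is dilution of an effect confined to one stratum (42% power at 0.8 SD, 60% at 1.0 SD), so the within-stratum estimates must be reported beside it.

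Two neighbouring gaps should be raised separately. Section 3 names two windows, "measured in the PACU and in the first 24 hours following surgery", and one should be made primary. Section 9 also says "A mid-point analysis was proposed after the study of 40 subjects" without saying whether that look tests efficacy; if it did, at 5% both times, the overall error would be about 8.3%.

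### Tukey's HSD over four groups spends the error rate on six pairs although only two are randomised; name the stratified treatment effect and the two randomised contrasts instead

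*Combined protocol and SAP*

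**What the plan says.** Section 9 is the whole analysis plan for the primary outcome: "ANOVA analysis using Tukey's HSD for post-hoc analysis for primary outcome data". It does not say whether the ANOVA is one-way or two-way, which factors enter, which pairs are of interest, or what happens if variances differ. It gives no alpha, SD, effect size or power.

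The design is clear elsewhere. In Section 5, "patients will be identified and initially stratified into two groups based on preoperative opioid use", and then "These two groups will then be each randomized (envelope assignment) into receiving either baclofen" or placebo, "such that there will be 4 groups of 20 patients identified". Section 6 confirms how the envelopes are arranged: "Groups 1&2 intermixed; Groups 3&4 intermixed". The Section 3 hypothesis concerns the drug and names no stratum: "We hypothesized that a single, oral dose of baclofen given to patients undergoing kidney stone surgery will reduce postoperative opioid requirements". Section 1 explains the stratification by a history of opioid use, "which would be expected to alter postoperative pain medication requirements".

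**The concern.** On a factor with two levels, Tukey's HSD has one pair and reduces to the ordinary t-test. Naming it makes sense only for the four groups, where it covers every pair. Four of those pairs compare tolerant with naive patients. Those comparisons are not randomised, and Section 3 does not ask about them. The price of covering them is paid by the two comparisons that are randomised.

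The main thing at stake is power within strata, in a trial with only 20 patients per group. A second issue is conditional. Tukey uses one pooled error variance. If opioid consumption varies more in one stratum, that variance is too small for the more variable stratum and too large for the other. The two randomised contrasts are then not tested at the same level.

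**Working it through.** **Inputs from the documents.** Four groups of 20 (Section 5), so 80 patients and 80 − 4 = 76 error degrees of freedom. Randomised pairs: 1 v 2 and 3 v 4 (Sections 5 and 6).

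**Assumptions, because the documents give no figure.** Two-sided 5% error, normal data, one analysis at full size, effects in SD units (0.8 for illustration), and tolerant:naive SD ratios of 1 to 3. The plan states no power figure to reproduce.

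**Step 1: the price of six pairs.**
- Pairs among four groups: 4 × 3 / 2 = 6, of which 2 are randomised.
- Tukey cut-off: q(0.95; 4, 76) = 3.715, and 3.715 / √2 = 2.627 on the t scale.
- Two-sided level per pair: P(|t76| > 2.627) = 1.04%.
- The two randomised pairs together: 1 − (1 − 0.0104)² = 2.1%.
- Bonferroni on two pairs: |t| > 2.287. A single contrast: |t| > 1.992.

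**Step 2: power with equal SDs (noncentral t).**
- Within a stratum: SE = √(2/20) = 0.316 SD, so the noncentrality at 0.8 SD is 0.8 / 0.316 = 2.53.
- Treatment effect over both strata: SE = √(1/20) = 0.224 SD, so the noncentrality is 0.8 / 0.224 = 3.58.

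| Test | Power at 0.8 SD | Difference detectable with 80% power |
|---|---|---|
| Tukey, one stratum | 46.6% | 1.10 SD |
| Bonferroni on two contrasts, one stratum | 59.7% | 0.99 SD |
| Stratified treatment effect, benefit in both strata | 94.2% | 0.63 SD |

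By simulation, two Welch tests with Holm give 64-65% per stratum if both strata benefit and 58% if one does. Keeping six pairs and changing only the variance handling (Games-Howell) gives 45%. The gain therefore comes from testing two contrasts, not from the variance method.

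**Step 3: unequal spread (conditional).** Take an SD of 2 in tolerant and 1 in naive patients. The pooled variance is (4 + 1)/2 = 2.5, so the pooled SD is 1.58.
- Tolerant: the true SE is 2/1.58 = 1.26 times the one used, so the working cut-off falls to about 2.627/1.265 = 2.08.
- Naive: the true SE is 1/1.58 of the one used, so the working cut-off rises to about 2.627 × 1.58 = 4.15.

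Simulated null error per contrast under Tukey, against a nominal 1.0%:

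| SD ratio | Tolerant | Naive | Either |
|---|---|---|---|
| 1.5 | 2.8% | 0.14% | 3.0% |
| 2 | 4.3% | 0.01% | 4.3% |
| 3 | 5.7% | about 0% | 5.7% |

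If naive patients vary more, the direction reverses. Two contrasts with the pooled error kept would give 6.0%, 7.6% and 9.6% for either contrast at these ratios, so the change of contrasts and the change of variance belong together.

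**Step 4: does this create a one-stratum pattern?** It depends on the effect scale. At SD ratio 2:
- Equal effect of 0.8 of each stratum's own SD: Tukey gives tolerant-only results in 63% of trials and naive-only in 2%.
- Equal mg reduction (0.8 pooled SD): Tukey gives 25% and 22%. Welch-Holm, if performed only after a significant treatment effect, gives 1% and 43%, while the interaction is significant in 5%.

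**Step 5: should the within-stratum tests wait for a significant treatment effect?** With equal SDs and benefit of 0.8 SD in one stratum only, the average effect is 0.4 SD. The noncentrality is 0.4/0.224 = 1.79, and the treatment effect then has about 42% power. Power to find the benefiting stratum is 36% with that condition, 58% without it, and 46-47% with Tukey.

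**The case against.** The strongest reply is that little is broken. Section 9 calls Tukey a post-hoc step. A two-way ANOVA would already contain the treatment effect that Section 3 needs, and that effect keeps about 5% error. With equal spread, Tukey is valid and conservative. All of this stands, and it limits the point to efficiency and specification. It does not remove the point, because Section 9 names neither the two-way model nor the treatment effect as the primary test.

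A reader might infer that Tukey inflates false claims. The figures do not support that as the main harm: a false claim in either randomised contrast stays between 2.1% and 4.3% up to SD ratio 2, and passes 5% only at the assumed ratio of 3.

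A reader might also infer that a tolerant-only result would be an artefact of the method. The documents do not support this either. Section 1 expects requirements to differ by opioid history but gives no SD and no direction for the spread, and nothing says whether the effect should be constant in mg, percent or SD units. For an equal mg reduction Tukey is near balanced, and the Welch tests are the lopsided ones.

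**Conclusion.** The point holds as an inexpensive improvement to consider, not as an error that invalidates the trial. On the four-group reading, Tukey gives 47% power per stratum at 0.8 SD, where two named contrasts give 60% (Bonferroni) or 58-65% (Welch with Holm, depending on whether one or both strata benefit). That rests on 20 per group, equal SDs, a two-sided 5% level and one analysis; Section 9 also mentions a look at 40 subjects, which is a separate matter. The six-pair count needs no variance assumption.

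The variance part is conditional on an SD ratio found nowhere in the documents. What it supports is unequal calibration of the two contrasts, not a prediction that one stratum will falsely appear to respond. If the sponsor intended a two-way ANOVA with the treatment effect as the primary test, the analysis for Section 3 is sound, and only the wording and the follow-up comparisons need attention.

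**What to change.** In Section 9:

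1. Make the primary test the baclofen v placebo effect in an ANOVA with treatment and opioid stratum.
2. Replace Tukey with the two randomised contrasts, Groups 1 v 2 and 3 v 4, by Welch tests with Holm adjustment. Report each confidence interval from its own stratum's variance.
3. Judge a difference between strata by the treatment-by-stratum interaction on a stated scale (mg difference or ratio), not by which stratum reaches significance.
4. State before unblinding whether the within-stratum tests are supportive or carry their own claim. Making them conditional on a significant treatment effect is optional, because it loses power against Tukey when only one stratum benefits (36% v 46-47% at equal SDs).

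No patients, procedures or data are added, but there are costs:
- Adjusted tolerant v naive comparisons are given up.
- If tolerant patients vary more, power in that stratum at SD ratio 2 is slightly below Tukey's inflated figure when both strata benefit (65% v 68%), and further below it when only tolerant patients benefit (58% v 68%).
- Unconditional within-stratum tests beside the treatment effect raise the chance of any false claim to about 8%, unless they carry no confirmatory claim.
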